Additionally, a home-based strategy will also be utilized in order to assess preferences around recruitment venue, and to ascertain which seek strategy will identify the highest number of HIV positive female youths. Home-based HIV testing services has been provided in Kenya to individuals and families since 2006 and was piloted in Nyanza Province, with a high acceptance rate above 90% (NASCOP, 2008). Home-based testing is efficient and confidential, with high uptake. Over 80% of KAIS 2012 survey participants who had never tested for HIV, accepted home-based testing services; with 81.6% acceptance among female youth aged 15-19 years, and 79.3 % in the 20-24 age group (NASCOP, 2014a). With any home-based approach, community entry procedures will be observed and we will follow home-based testing services protocols and guidelines that have been established by the Government of Kenya. Study team leadership are experienced in home-based HTS delivery in a rural setting (PIs: [name], [name], Co-I: [name], R01HD058363). The home-based and community-based recruitment strategies used in the study is a departure from the more passive approach to HTS that is conducted in antenatal clinics, health facilities, and research clinic settings. HIV testing services and recruitment for research has traditionally been done in health facilities. Due to financial, health system, cultural, and knowledge barriers experienced by adolescents, young women are unlikely to access standard facility based HTS. Therefore, our study offers HIV testing and recruitment in different settings in order to inform best practices regarding HIV and recruitment strategies targeting this population.

Rationale for self-testing

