11.3 Eligibility Determination (Inclusion/Exclusion) and Enrollment

Participants will be screened for eligibility by Research Assistants or other study staff. Participants must meet all inclusion criteria and may not meet any exclusion criteria in order to be eligible to participate in the study.

Eligibility Requirements:

Inclusion Criteria:

- Female between the ages of 15-24.
- Able to understand spoken English or Kiswahili or Dholuo.
- Resides in Homa Bay County.
- Not previously diagnosed as HIV positive.
- Willing to give informed consent or if younger than 18 years of age and not an emancipated minor, has a parent or guardian willing to provide consent in addition to the minor's assent.

Exclusion Criteria:

- Male.
- Unable to understand spoken English, or Kiswahili or Dholuo.
- Females who are older or younger than the ages of 15-24.
- Resides outside of Homa Bay County.
- HIV positive.
- If under 18 and not an emancipated minor, unable to get parental consent.

Enrollment

After eligibility is assessed/confirmed, participants will be offered enrollment using the approved recruitment script. If she agrees, she will be taken through the following study enrollment procedures: (1) completing registration (to generate a study ID and to ensure single enrollment); and (2) completing the baseline behavioral survey using the tablet computer. Once enrolled, the participant will choose her preferred HIV testing options: (1) oral fluid HIV self-testing at her convenience, (2) HIV testing services (HTS) by study staff at the recruitment location, or (3) a referral to a health care facility for standard HTS. Participants who elect self-testing will be given the self-test kit and will be taken through the self-testing counseling using visual aids (either in the home or in the community). For participants who select staff administered HTS, the test will be conducted by the study staff. For participants who request a referral for HTS at a health facility, they will be given a referral card with the name of a staffer (or other contact to be determined) at the facility. All participants will complete the participant assessment tracking form (this includes locator information for follow-up).

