- Primary Prevention (N≈185):
 - Proportion reporting HIV risk behaviors, and condom use, at 6 and 12 months;
 - Proportion who re-tested at 12 months.
 - Proportion with a positive HIV test result for a sub-set of negatives at 12 months.

Statistical Analyses

Recruitment Strategy and Testing Modality: We will determine which HIV testing approaches are most preferred among all female youth and among higher risk female youth. We also will determine which recruitment and HIV testing approaches yield the highest rates of newly diagnosed HIV infection. Multinomial logistic regression (Hosmer & Lemeshow, 2004; Hosmer, Lemeshow, & Sturdivant, 2000) will be used to understand which testing approaches are most preferred/used by female youth. Preference for HIV testing at a health facility will be the reference category for the dependent variable. A model with only an intercept will be used to estimate the proportion of girls preferring each testing approach, and to test for pairwise differences in preferences (e.g., does a higher proportion of girls prefer staff-aided rather than self-testing?). In addition to overall preferences, we will consider age, risk behaviors, and HIV testing history as predictors of preferences by adding participant characteristics to the multinomial logistic regression analysis. Type of testing selected by participants, including refusal to test, will be regressed on predictors to estimate how characteristics of female youth impact HIV testing preferences. Model coefficients will describe the change in odds of preferring other types of testing relative to the reference category (facility-based testing).

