Logistic regression analysis will be used to determine which recruitment and HIV testing approaches yield the highest proportion of newly diagnosed HIV infection. HIV testing result (negative vs. positive) will be regressed on variables indicating recruitment strategy (home vs. community) and type of HIV testing (self, staff-aided, facility-based). With facility-based testing following community-based recruitment as a reference category, we will estimate how home-based recruitment and other testing approaches change the odds of a positive test result. The interaction between recruitment strategy and HIV testing approach will be tested to determine whether the yield of each testing approach is conditional on recruitment strategy. If a significant interaction effect is found, simple main effects of testing approach within each recruitment strategy and simple main effects of recruitment strategy within each testing approach will be estimated. In addition to comparing yield by recruitment strategies and testing approaches, we will consider interaction effects with youth characteristics, such as age, risk behaviors, and HIV testing history, and type of testing. Similar logistic regression analyses will examine differences in the odds of completing all confirmatory testing by recruitment strategy and approach to testing.

Home-based and community-based recruitment strategies will also be compared to determine which strategy is more effective in reaching higher risk female youth. Rates of acceptance of screening among potential participants offered screening and rates of enrollment among eligible participants will be compared by recruitment strategy using logistic regression. Risk will be characterized by number and serostatus of sex partners, concurrency, condom use, and patterns of HIV testing by the participant and any sex partners.

A random selection of N≈185 girls with HIV negative tests will be followed-up. We will assess risk behaviors, condom use, additional HIV testing, linkage to prevention and any new HIV diagnoses over the year since study enrollment. Re-testing, prevention service use, and new HIV will be examined in relation to recruitment strategy, testing approach at enrollment, and participant risk behavior and other characteristics.

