15.11 Sample Size Considerations

Baseline sample size calculation

Based on our experience with MP3 Youth (data not yet published), which screened N=788 female youth and enrolled N=690 female youth over a period of eight months (November 19, 2014 – June 12, 2015), we expect we can recruit N=1200 female youth over a period of around twice that time. We expect the sample accrual rate to be slower than in MP3 Youth, because we will be recruiting only female youth and mainly those out of school (a large proportion of younger MP3 Youth girls were in school and easier to recruit). In addition, we have two different recruitment strategies, and the home-based strategy may be more labor intensive and time consuming than a community mobile event. We therefore expect a somewhat lower accrual rate. Therefore, in order to stay within the estimate 12 months of recruitment, we will increase our field staff during the implementation phase of the project. Sample size estimates are also based on IRDO's program data and the estimated number of youth in Homa Bay. We expect large numbers of youth will be successfully recruited from the home and mobile events (IRDO reaches tens of thousands of youth/year) for a total sample size of ≥ 1200 female youth.

Power Analysis

Power calculations for Aim 1 are based on the yield of newly diagnosed HIV across recruitment strategies and testing options offered to female youth. Using version 12 of the PASS program (Hintze, 2013) for logistic regression, we did not approach this power analysis from the perspective of calculating a sample size needed to detect a particular effect size with at least 80% power. Rather, because this part of the study (Aim 1) is not a clinical trial but rather an exploration of preferences and yield of recruitment and participant-selected testing strategies, we started with the large, feasible sample size and determined the size of effects that could be detected with at least 80% power when comparing recruitment strategies and HIV testing approaches.

The expected percentage of girls testing positive is based on our MP3 Youth pilot study. In that study, 55 of 636 female youth not previously diagnosed were found to have HIV infection (data not yet published). Thus, we expect about 9% of all tested females in this study to have HIV infection not previously diagnosed.

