With this estimate of the expected percentage of girls with newly diagnosed HIV infection, we asked how small of an increase in the odds of newly diagnosed HIV infection could be detected with 80% power when community-based recruitment is compared to home-based recruitment. With 600 youth recruited by each strategy, power is 80% to detect an odds ratio of 1.67, in other words, a modest increase from 9% to 14% newly diagnosed with HIV infection. When comparing testing approaches, and assuming an equal proportion of girls prefers each approach and testing approach does not interact with recruitment strategy, power is 80% to detect an odds ratio of 1.85. If there is an interaction between recruitment strategy and testing approach, when comparing

testing approaches within a recruitment strategy (i.e., estimating simple main effects), power is 80% to detect an odds ratio of 2.32.

These calculations show the proposed sample size (N=1200) is capable of detecting modest differences in the yield of newly diagnosed HIV infection across both recruitment strategies and testing approaches.

Among the approximately 108 female youth we expect to be newly diagnosed with HIV infection, about 20% are expected to successfully initiate HIV care at a health facility after a single SMS message. The remaining 80% (N=86) who are not linked to care after the initial SMS message will be randomly assigned to either continued SMS messages or to economic incentives. Assuming at least 60% are linked to care at some point during follow-up, survival analysis employing Cox regression will be able to detect a hazard ratio of 2.2 describing the impact of treatment condition (continued SMS vs. economic incentives) on the occurrence and timing of successful linkage to care at a health facility, with 80% power.

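### The 80% power for yield by testing approach holds only if one third of girls choose and complete each option, and facility testing, the likely smallest group, is the yield model's reference

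*Combined protocol and SAP*

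**What the plan says.** Comparing the yield of new HIV diagnoses across the three testing options is part of the first primary objective (section 8). The option is not allocated. Section 11.3 states: "Once enrolled, the participant will choose her preferred HIV testing options".

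The power analysis in section 15.11 starts from a baseline yield: "we expect about 9% of all tested females in this study to have HIV infection not previously diagnosed". For recruitment it says: "With 600 youth recruited by each strategy, power is 80% to detect an odds ratio of 1.67". For testing approach it gives 80% power at an odds ratio of 1.85, "assuming an equal proportion of girls prefers each approach" and that there is no interaction with recruitment strategy. If there is an interaction, it gives 2.32 within a recruitment strategy and does not repeat the equal-split condition. It then concludes that N=1200 can detect modest differences in yield across both recruitment strategies and testing approaches. Section 10.2 draws the same conclusion without mentioning an equal split, and gives 2.01 rather than 2.32 for the within-strategy comparison.

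On facility testing, section 7.4 says that "young women are unlikely to access standard facility based HTS", citing several kinds of barrier. The yield model in section 13.2 is set up "With facility-based testing following community-based recruitment as a reference category".

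**The concern.** A detectable odds ratio depends on the sizes of the two groups compared. Here those sizes depend on what girls choose and whether they then test. The plan offers no basis for equal thirds, and its own rationale points towards a small facility group. Because that group is the reference, both testing-approach coefficients in the yield model are contrasts with it, so an imbalance costs most in the comparisons that the model reports by default.

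At stake is how a primary-objective result is read. Someone relying on section 10.2, where the condition does not appear, could take a non-significant contrast with facility testing as evidence of similar yield when the comparison had little power.

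**Working it through.** **Inputs.** N = 1200, 600 per recruitment strategy, reference yield 9% and the stated odds ratios all come from section 15.11. Alpha and sidedness are not stated. Two-sided 0.05 is assumed, and it reproduces all three figures in that section (one-sided 0.05 gives about 88% power at each).

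**Formula.** With p1 = 0.09 and p2 = OR × p1 / (1 − p1 + OR × p1):

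power = Φ{ [ |p2 − p1| − 1.96 × √( p̄(1 − p̄)(1/n1 + 1/n2) ) ] / √( p1(1 − p1)/n1 + p2(1 − p2)/n2 ) },

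where p̄ is the pooled proportion weighted by group size.

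**Step 1: reproduce the plan's figures.**

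| Comparison | Groups | OR | p2 | Power |
|---|---|---|---|---|
| Recruitment | 600 v 600 | 1.67 | 14.2% | 80.0% |
| Testing, pooled | 400 v 400 | 1.85 | 15.5% | 79.8% |
| Testing, within strategy | 200 v 200 | 2.32 | 18.7% | 80.2% |

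The arithmetic is right. The last row shows that 2.32 also rests on equal thirds.

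**Step 2: vary the facility share.** The documents give no share, so this is an assumed range. Facility yield stays at 9% and the remaining girls are split equally between self-testing and staff-aided testing.

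Worked case, 10% share, pooled (120 v 540) at OR 1.85:
- p̄ = (120 × 0.09 + 540 × 0.1547)/660 = 0.1429
- Null standard error = √(0.1429 × 0.8571 × (1/120 + 1/540)) = 0.0353
- Alternative standard error = √(0.09 × 0.91/120 + 0.1547 × 0.8453/540) = 0.0304
- Power = Φ[(0.0647 − 1.96 × 0.0353)/0.0304] = Φ(−0.15) = 44%

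| Facility share | Pooled groups | Power at 1.85 | Detectable OR | Within-strategy groups | Power at 2.32 | Detectable OR |
|---|---|---|---|---|---|---|
| 33% | 400 v 400 | 80% | 1.85 | 200 v 200 | 80% | 2.32 |
| 25% | 300 v 450 | 75% | 1.92 | 150 v 225 | 75% | 2.43 |
| 20% | 240 v 480 | 69% | 2.00 | 120 v 240 | 68% | 2.56 |
| 10% | 120 v 540 | 44% | 2.39 | 60 v 270 | 43% | 3.25 |
| 5% | 60 v 570 | 23% | 3.10 | 30 v 285 | 20% | 4.55 |

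**Step 3: the contrast that gains.** Staff-aided versus self-testing at OR 1.85 has 84% power at a 25% facility share (450 v 450), 90% at 10% (540 v 540, detectable OR 1.71) and 92% at 5% (570 v 570).

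**Step 4: completion.** The outcome is a test result, and a girl who chooses facility testing leaves with a referral card. If one third choose it but half of them never test (an assumption), the contrast is 200 v 400 and power at OR 1.85 is 60%.

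**Step 5: the figure in section 10.2.** At 200 per option, OR 2.01 has 62% power. It reaches 80% (79.6%) at about 300 per group, which is not the within-strategy group size under equal thirds.

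**The case against.** The strongest reply is that this is a disclosed planning assumption, not a mistake in calculation. Section 15.11 states the equal split in the same sentence as 1.85. Sections 10.2 and 15.11 call Aim 1 an exploration rather than a clinical trial, with N set by feasibility and detectable effects worked out afterwards. All of that stands. It does not cover section 10.2, where the condition is missing, or the unqualified conclusion in both sections.

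A reader might infer that the stated power is simply not delivered. The documents do not support that. Section 7.4 concerns access to facility services in general, not choice when staff offer all three options with a referral card and a facility contact, and it gives no share. At 25% the loss is about 5 points. If facility testers had the higher yield, power at a 10% share would be 55.5% rather than 44%.

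A reader might also infer that every odds ratio in the plan runs against facility testing. It does not. The recruitment main effect does not depend on the testing split. If the interaction is significant, section 13.2 already plans simple effects of recruitment within each testing approach. The preference model does state "Preference for HIV testing at a health facility will be the reference category for the dependent variable", but pairwise preference tests are planned there, including staff-aided against self-testing, and the power figures concern yield, not preference.

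Finally, changing the reference category does not alter model fit, and standard facility testing is a legitimate comparator. Staff-aided versus self-testing can be derived from the yield model as planned. It is just not listed.

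**Conclusion.** The concern holds in conditional form. The figures 1.85 and 2.32 are arithmetically correct under equal thirds, but a design in which girls choose does not secure equal thirds, and the protocol's own rationale gives reason to doubt them. If fewer than one third choose and complete facility testing, contrasts with facility testing have less than 80% power at the stated odds ratios. The shortfall runs from about 5 points at a 25% share to more than half the stated power at 5%.

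These sizes rest on assumed shares, 9% yield in the facility group, two-sided 0.05, an equal split of the remainder and, except in the completion example, every girl being tested. The recruitment comparison and the preference model are unaffected, and staff-aided versus self-testing does better than stated. The separate disagreement between 2.01 and 2.32 needs no assumption about shares: the two sections give different values for the same comparison.

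**What to change.** **Sections 10.2 and 15.11**
- State that the testing-approach figures, including 2.32, assume one third of girls choose and complete each option.
- Add detectable odds ratios over a range of facility shares (for example 33%, 25%, 20%, 10% and 5%) for each pairwise contrast.
- Limit the claim of modest differences to the contrasts that support it.
- Reconcile 2.01 with 2.32, and state alpha and sidedness.

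**Section 13.2**
- Prespecify all three pairwise yield contrasts, with staff-aided versus self-testing named. Changing the reference category is optional.

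The cost is wording and less favourable figures for contrasts with facility testing. No extra participants or data are needed.
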